Preliminary work relevant to the Aims of the proposed study: To test whether mtDNA is released in response to psychological stress, we conducted a preliminary uncontrolled laboratory study assessing levels of ccf-mtDNA before and after an acute (5-min) socio-evaluative stressor on two separate occasions. The stressor was chosen for its ability to evoke glucocorticoid hormone release and reliably stimulate increases in circulating markers of inflammation, which typically peak 1-2 hours post-stress. We developed a rigorous approach to quantify serum levels of two mtDNA genes (CYTB and ND1) in 50 healthy midlife individuals (mean age = 50 years, range: 41-58). Serum was collected at baseline (pre) and immediately (post) and 30 minutes after stress (+30 min). DNA was isolated and analyzed by a blinded operator and normalized to a standard curve.

Ccf-mtDNA levels dramatically increased +30 min after the stressor, exhibiting a large effect size ($\eta^2 = .556$, $P < 0.0001$, Figures in Research Plan), with 93% of participants showing an increase in ccf-mtDNA (CYTB). This result was replicated at a second visit, yielding similar results and a comparable effect size. Analyses of the second amplicon ND1 confirmed these findings at both sessions. Findings provide robust initial evidence for psychological stress-induced increases in the highly immunogenic molecule, ccf-mtDNA, but did not establish the time kinetics, the maximal amplitude of this response, or the association of this response with later increases in inflammatory mediators. These are gaps in our knowledge that will be examined in the proposed study.

Both mitochondrial and nuclear genomic fragments can be found in blood. Prior evidence shows that exhaustive physical exercise is followed by increases in both ccf-mtDNA and nuclear-derived ccf-nDNA, possibly due to tissue damage. To ascertain whether psychological stress-induced ccf-mtDNA could result from unspecific cellular damage and non-specific bulk cellular

material release, we also assessed two nuclear gene markers in our preliminary work. In contrast to ccf-mtDNA, ccf-nDNA (GUSB) was unchanged at +30 min on both occasions of testing. Accordingly, at +30 min after stress the ratio of circulating mitochondrial to nuclear genome mtDNA/nDNA rose by >2-fold.

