Specific Aim 1 (human stress study). Determine the temporal relationship between psychological stress, ccf-mtDNA, and systemic inflammation. We hypothesize that socioevaluative stress will trigger robust and transient ccf-mtDNA release compared to a non-stressed condition. To test this, 60 volunteers (50% female; aged 20-50) will be tested on two occasions separated by at least 1 month. On one occasion, they will be exposed to the a socio-evaluative speech stressor known to elicit increases in circulating markers of inflammation at 40-90 minutes. On the other occasion, they will rest quietly for the same period of time. Conditions will be counterbalanced across subjects and blood drawn at ten time points over two hours. We expect that the stress task will induce a specific increase in ccf-mtDNA, which will statistically mediate subsequent peak circulating IL-6 and TNF- α levels. To validate that the stress task was associated with physiological arousal, we will examine task-related changes in heart rate, blood pressure, heart rate variability, and circulating levels of cortisol, epinephrine, and norepinephrine. This study will establish the kinetics and magnitude of psychological stress-induced ccf-mtDNA release, and whether ccf-mtDNA mediates the inflammatory response to acute stress in humans.

Study Design & Methods

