At both visits, participants will be situated upright in a comfortable chair, where an intravenous catheter will be inserted into the antecubital fossa of one arm for collection of blood samples. Next, a blood pressure cuff (Dinamap) will be placed on the opposite arm from the catheter. Research staff will then apply 11 skin surface electrodes to permit the assessment of heart rate variability [HRV]. Electrodes will be applied to the skin (on the back of the neck, upper chest, shoulders, ribs, and calf area below the knee). The electrodes are the same as those used to record a person's EKG. HRV will be derived from the EKG signal. Following instrumentation, participants will sit quietly for a 30-minute baseline (habituation) period before completing either the speech task or a rest period. Following this, participants will watch a wildlife documentary and complete questionnaires for a 120-min recovery period. Blood samples will be collected at mins. -5 (end of baseline/habituation), and +5, 10, 20, 30, 45, 60, 75, 90, and 120 post the task period. Blood pressure will be recorded twice prior to each of the 10 blood draws. Participants will also complete the Brief Profile of mood State questionnaire on 4 occasions, immediately pre- and post-task, and at 60- and 120-minutes post task. This 39-item adjective checklist provides a measure of emotional state. These time points were chosen to capture both acute and delayed neuroendocrine and inflammatory changes, as well as recovery patterns following standard schedules in the literature.

At one visit, participants will be exposed to the speech task. This is a widely used, highly effective way to investigate stress responses in a laboratory setting. It induces significant increases in cortisol, indices of autonomic activation, and circulating levels of inflammatory mediators. Our preliminary data provides novel evidence that this stressor also results in increased cc-mtDNA. Participants will be told that they will give a speech, recorded by a video camera and in front of an audience (two research staff) trained to assess non-verbal behaviors.

Participants will be given 2 minutes to prepare for the speech defending themselves against an alleged transgression and 3 minutes to deliver it. At the end of the recovery period following the task, all participants will be thoroughly debriefed.

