Univariate and descriptive analysis will be performed on all dependent variables and, if necessary, normalizing and/or variance stabilizing transformations will be applied to the data before inferential analyses are undertaken. All hypothesis testing will involve two-sided alternative hypotheses with the α level set to 0.05. The analytic strategy for addressing Aim 1 will involve fitting linear mixed models, which allow flexible covariance structures to account for correlation of repeated measures data. Specifically, subject and day (nested within subject) will be the random effects, and condition (stress/control) along with other covariates will be the fixed effects. We will also include time and time 2 (squared) as fixed effects to allow for a nonlinear response. The outcome variables will be the various physiological and psychological responses:

IL-6, TNF- α , ccf-mtDNA, cortisol, epinephrine, norepinephrine HR, BP, momentary negative affect, and HRV.

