## Statistical Plan and Power

Power: For the primary analysis, because we are utilizing a “matched” design (in which each subject serves as his/her own control), we based our power calculations on a simple paired t-test since power formulas are not available for complex models such as the ones we propose to apply to our data. We determined that with the sample size  $n = 60$ , we would have 80% power to detect a normalized difference (in terms of Cohen’s  $d$ ) as small as 0.38. Combined effects sizes from a meta-analysis of the literature [1] yield normalized effect sizes for IL-6 and TNF- $\alpha$  at 0.35 and 0.28, respectively. For ccf-mtDNA, our pilot data gave an estimated effect size of 1.13. Thus, with a sample of  $N=60$ , we were sufficiently powered to detect stress-induced changes. In fact, the collection and modelling of multiple measurements over time. With multiple observations, accounting for the correlation structure among repeated observations, we would increase the power of the analysis to detect a change.

Univariate and descriptive analysis will be performed on all dependent variables and, if necessary, normalizing and/or variance stabilizing transformations will be applied to the data before inferential analyses are undertaken. All hypothesis testing will involve two-sided alternative hypotheses with the  $\alpha$  level set to 0.05. The analytic strategy for addressing the laboratory stress session will involve fitting linear mixed models, which allow flexible covariance structures to account for correlation of repeated measures data. Specifically, subject and day (nested within subject) will be the random effects, and condition (stress/control) will be the fixed effects. We will also include time and time $^2$  (when indicated) as fixed effects to allow for a nonlinear response. The outcome variables will be the various physiological and psychological responses: IL-6, TNF $\alpha$ , ccf-mtDNA, cortisol, epinephrine, norepinephrine HR, BP, momentary negative affect, and HRV.

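### Linear plus optional quadratic time is too rigid a curve for the kinetics and magnitude that Aim 1 promises; how far it distorts them depends on a response shape that the documents do not give

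*Protocol*

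**What the plan says.** The Protocol, under Statistical Considerations, fits linear mixed models to every listed outcome. The fixed part is given as "condition (stress/control) along with other covariates will be the fixed effects", followed by "We will also include time and time 2 (squared) as fixed effects to allow for a nonlinear response". The random part is given as "subject and day (nested within subject) will be the random effects", and the models are described as ones "which allow flexible covariance structures to account for correlation of repeated measures data", with no structure named.

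The SAP, under Statistical Plan and Power, repeats this with one change. The squared term enters only "when indicated) as fixed effects to allow for a nonlinear response" (the opening bracket falls before these words), and no criterion is given.

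Neither document states the unit or coding of time, a condition-by-time interaction, or a categorical, spline or piecewise alternative.

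On purpose, Specific Aim 1 says: "This study will establish the kinetics and magnitude of psychological stress-induced ccf-mtDNA release". It also expects the release to be transient. Study Design & Methods schedules ten samples, one at -5 min and the rest at +"5, 10, 20, 30, 45, 60, 75, 90, and 120 post the task period".

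On what is already known, the preliminary work in the Protocol's background says: "Serum was collected at baseline (pre) and immediately (post) and 30 minutes after stress (+30 min"). The same section states that the pilot left the time course and the maximum of the response open.

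**The concern.** The ten samples are dense early (five by +30 min) and sparse late (five from +45 to +120 min). The expected response is flat before the task, rises quickly and recovers. A parabola in minutes has one turning point and equal slopes on either side of it. To follow a long recovery it must move its turning point later. To pass near the early high values it must lift its fitted value at the pre-task sample. Both errors fall on the quantities of interest: the fitted peak time is wrong, and the fitted rise from baseline is too small because the fitted baseline is too high. If the squared term is dropped, the fit is a straight line with no peak between the first and last samples.

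This is a matter of curve shape. Adding a condition-by-time interaction to the quadratic would not cure it, because each condition would still be forced onto a parabola. At stake is the descriptive core of Aim 1, which is when ccf-mtDNA peaks and by how much it rises.

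**Working it through.** The documents give no fitted peak time or rise, so there is no figure of the plan's own to reproduce here. The power statement concerns a paired difference and does not bear on the curve.

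**Inputs from the documents.** Sampling times t = -5, 5, 10, 20, 30, 45, 60, 75, 90, 120 min; mean model linear plus quadratic in time; 60 participants, 2 visits, 10 samples.

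**Assumptions, not in the documents.** The shape and peak time of the true stress-minus-rest curve; time coded in minutes; a separate curve for each condition. The main case is a gamma-type curve y = (u·exp(1 - u))^k with u = (t - onset)/(peak - onset), baseline 0, true peak 1, k = 1 to 4, onset -5 or 0 min. Curves are noise-free, so any discrepancy is pure misfit.

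**Method.** Fit b0 + b1·t + b2·t² by least squares at the ten times. With balanced data and random intercepts, the mixed model gives the same time coefficients. Fitted peak time = -b1/(2·b2). Fitted rise = fit at that time minus fit at -5 min.

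**One case in full (peak +30, k = 2, onset -5).**
- True values at the ten times: 0, 0.341, 0.576, 0.903, 1, 0.866, 0.621, 0.399, 0.239, 0.075.
- Fit: 0.3546 + 0.01708·t - 0.0001765·t².
- Peak time: 0.01708/(2 × 0.0001765) = +48.4 min, against a true +30.
- Fitted maximum: 0.77. Fit at -5 min: 0.26, against a true 0. Fitted rise: 0.50, against a true 1.

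**Gamma-type curves by assumed peak time (k = 1 to 4, both onsets).**

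| True peak (min) | Fitted peak (min) | Fitted rise (true 1) |
|---|---|---|
| +10 | maximum at -5 | none above the pre-task sample |
| +20 | +17.8 to +38.0 | 0.03 to 0.24 |
| +30 | +46.5 to +52.0 | 0.39 to 0.59 |
| +45 | +58.4 to +63.5 | 0.82 to 0.95 |
| +60 | +68.5 to +72.8 | 0.93 to 1.1 |

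For the +30 row, R² runs from 0.38 to 0.66.

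**Other transient shapes, all with a true peak of 1 at +30.**

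| Shape | Fitted peak (min) | Fitted rise |
|---|---|---|
| Triangle, back to baseline at 60 to 150 min | +35.7 to +58.5 | 0.15 to 0.77 |
| Triangle, over by 45 min | +20.6 | 0.03 |
| Linear rise, exponential decay, half-life 10 to 60 min | +37.6 to +60.2 | 0.16 to 0.72 |
| Log-normal, s = 0.3 to 1.0 | +46.5 to +58.4 | 0.25 to 0.73 |
| Bell curve, SD 10 to 15 min | +34.2 to +40.1 | 0.15 to 0.17 |

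A fall to a plateau at 25 to 75% of the peak, which does not return to baseline, gives +55.3 to +71.8 and 0.58 to 0.90.

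**Sensitivity of the +30 gamma result.**
- Compound-symmetric errors: unchanged.
- Exponential within-visit correlation: about +49 to +62 min, rise 0.37 to 0.92.
- Log scale: +46.8 to +54.0 min, rise 0.44 to 0.62.
- Post-task samples only: fitted peak +39 to +44 min.
- Time coded as sample number: about +34 to +38 min, rise 0.72 to 0.87.
- Model exactly as written (no interaction) with a flat rest visit: both conditions share one curve with half the rise, about 0.39/2 = 0.20 to 0.59/2 = 0.30.

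**Comparison.** With categorical time crossed with condition, each noise-free curve that peaks at a sampled time is returned exactly, in both peak time and rise.

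**The case against.** Several points on the other side are sound.

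- **A reader might infer that the plan will misplace a known +30 min peak at about +50 min.** The documents do not support this. The +30 min sample was the last one in the pilot, so the peak may be later, and neither the gamma shape nor coding in minutes is stated. A later peak keeps most of its rise, and coding by sample number removes most of the shift.
- **A reader might infer that the order of ccf-mtDNA and cytokine peaks would be blurred or reversed**, because a fitted peak near +50 falls inside the Protocol's 40 to 90 min cytokine window. That sets a fitted peak against an unfitted window. IL-6 and TNF-α go through the same model and their fitted peaks also move later: in the gamma family a true +30 is fitted at about 46 to 52, +45 at about 58 to 64 and +60 at about 69 to 73. The order is preserved in these cases.
- **A reader might infer that the stress-versus-rest test is biased.** As written, condition is a main effect. With complete data at identical times in both visits, its estimate is the same whether time is linear, quadratic or categorical.
- **The plan does not say that peak time will be read off the parabola.** It also plans descriptive analysis of all outcomes, in which the observed means would show a peak. The SAP's conditional wording can fairly be read as keeping the squared term wherever there is curvature.

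These points limit the size of the concern but do not remove it. Descriptive means are not an inferential model of the kinetics, and the richest curve that the conditional wording allows is still a parabola. Not knowing the shape is a reason against prespecifying a rigid one, since the distortion then depends on the very quantity that the study sets out to learn.

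**Conclusion.** The concern holds as a mismatch between the stated time function and the stated aim. The direction of the error in peak time (late, in most of the +30 min cases tried) and the loss of rise follow from the parabola's symmetry and the uneven schedule. The size does not follow from the documents alone. For an assumed +30 min peak in minutes with condition-specific curves, it ranges from about +34 to +60 min and from near 0 to about 0.77 of the rise across transient shapes. The gamma-type case gives +46 to +52 min and 0.4 to 0.6; a response over by +45 min is the near-zero case and is fitted early. Distortion is worst for early peaks (+10 to +20 min). For peaks at +45 to +60 min it is mainly a delay of about 10 to 20 min.

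The plan should be changed before analysis. The concern does not threaten the average condition contrast, and it does not show that the temporal ordering would be wrong.

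**What to change.** In the SAP, replace the linear and optional squared time terms with the ten nominal sampling times as a categorical factor crossed with condition. A prespecified spline crossed with condition is an acceptable alternative. Define peak time and peak change from the -5 min sample as quantities derived from the fitted stress-minus-rest differences. Keep the quadratic as a sensitivity analysis, with the coding of time stated.

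The cost is wording and some degrees of freedom. Categorical time by condition uses 1 + 9 + 9 = 19 fixed-effect terms beyond the intercept, against 1 + 2 + 2 = 5 for a quadratic crossed with condition. That is 14 more, against up to 60 × 2 × 10 = 1,200 observations per blood marker. The condition-by-time test then has 9 degrees of freedom, so it is less focused than a single contrast, and peak time is resolved only to the nearest sampling time.

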## Statistical Plan and Power

Power: For the primary analysis, because we are utilizing a “matched” design (in which each subject serves as his/her own control), we based our power calculations on a simple paired t-test since power formulas are not available for complex models such as the ones we propose to apply to our data. We determined that with the sample size  $n = 60$ , we would have 80% power to detect a normalized difference (in terms of Cohen’s  $d$ ) as small as 0.38. Combined effects sizes from a meta-analysis of the literature [1] yield normalized effect sizes for IL-6 and TNF- $\alpha$  at 0.35 and 0.28, respectively. For ccf-mtDNA, our pilot data gave an estimated effect size of 1.13. Thus, with a sample of  $N=60$ , we were sufficiently powered to detect stress-induced changes. In fact, the collection and modelling of multiple measurements over time. With multiple observations, accounting for the correlation structure among repeated observations, we would increase the power of the analysis to detect a change.

Univariate and descriptive analysis will be performed on all dependent variables and, if necessary, normalizing and/or variance stabilizing transformations will be applied to the data before inferential analyses are undertaken. All hypothesis testing will involve two-sided alternative hypotheses with the  $\alpha$  level set to 0.05. The analytic strategy for addressing the laboratory stress session will involve fitting linear mixed models, which allow flexible covariance structures to account for correlation of repeated measures data. Specifically, subject and day (nested within subject) will be the random effects, and condition (stress/control) will be the fixed effects. We will also include time and time $^2$  (when indicated) as fixed effects to allow for a nonlinear response. The outcome variables will be the various physiological and psychological responses: IL-6, TNF $\alpha$ , ccf-mtDNA, cortisol, epinephrine, norepinephrine HR, BP, momentary negative affect, and HRV.

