The proposed study will examine physiologic responses to acute psychological challenge in the laboratory among healthy adults. It is widely accepted that there is an increase in circulating markers of inflammation following a single bout of laboratory stress. This increase in systemic inflammation is believed to contribute to the damaging health effect of psychological stress. However, to date the biological mechanisms by which psychological stress is transduced into inflammation are unclear. Our preliminary evidence suggests that mitochondrion may play a role, with stress-induced increases in circulating levels of mitochondria- derived signaling molecules that are known to modulate immune cell function and the production of pro-inflammatory cytokines.

To test this possibility, we plan to conduct a crossover experimental trial examining physiological responses to an evaluative speech task under laboratory conditions. We have previously used this task to induce physiological arousal. We plan to recruit 60 non-smoking volunteers (50% female, aged 20-50 years) and test them on two occasions separated by at least a month. On one occasion they will be exposed to the speech task. On the other occasion, they will rest quietly for the same period. Conditions will be counterbalanced. At both visits cardiovascular responses (heart rate, blood pressure, and heart rate variability) will be assessed as measures of autonomic activation before, during and after the task period. Participants will also have an intravenous catheter inserted and blood drawn at ten time points over the two-hour testing period on each occasion. Blood samples will be sent to laboratories at the University of Pittsburgh and at Columbia University for the assessment of mitochondria-derived signalling molecules, inflammatory markers, cortisol and catecholamine levels.

Study Objectives

Our overarching hypothesis is that psychosocial stress regulates ccf-mtDNA release, which, in turn, signals a proinflammatory response. We examine this hypothesis in parallel human and cell-based studies. The current Clinical Trial only covers Aim 1 of the parent grant, which is the human study.

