8. Current smokers (defined as having smoked a cigarette in the previous 3 months).
9. Current illicit drug use (defined as reported use of illicit drugs such as marijuana, cocaine or heroin in the previous 3 months).
10. Not fluent in English (have used English in everyday speaking and reading for at least 10 years)
11. Unable or unwilling to give informed consent
12. Unwilling to abstain from alcohol and vigorous exercise for 24 hours, from food and drinks (other than water) for 3 hours and from non-prescription medications (other than oral contraception) for 2 days prior to testing.

Statistical Considerations

For the primary analysis in Aim 1, because we are utilizing a “matched” design (in which each subject serves as his/her own control), we base our power calculations on a simple paired t-test since power formulas are not available for complex models such as the ones we propose to apply to our data. We find that with the proposed sample size $n = 60$, we have 80% power to detect a normalized difference (in terms of Cohen’s d) as small as 0.38. Combined effects sizes from a meta-analysis of the literature [1] yield normalized effect sizes for IL-6 and TNF- α at 0.35 and 0.28, respectively. For ccf-mtDNA, our pilot data give an estimated effect size of 1.13 (see Fig. 4), such that we will be sufficiently powered to detect stress-induced changes, and to detect statistically significant differences in ccf-mtDNA separately in women and in men. In fact, however, we will not have to rely on such a simple analysis, since we are collecting several measurements over time and will be modeling the entire trajectory. With multiple observations, by taking into account necessary covariates and accounting for the correlation structure among repeated observations, we will increase the power of the analysis to detect a change, potentially dramatically, and so we expect to be amply powered. For the secondary analyses, again we will be applying more sophisticated and powerful analyses, but for reference we base our power calculations on Pearson’s correlation analysis and find that with the proposed sample size we are powered to detect a “true” correlation coefficient as small as 0.35 (in absolute value), typically considered somewhere between a “small” and “medium” effect size.

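### The SAP calls N=60 sufficient without naming an outcome, but on its own paired t-test basis power is 76% for IL-6 and 57% for TNF-alpha

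*SAP*

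**What the plan says.** Both documents size the study on a paired comparison; in the SAP's words, "we based our power calculations on a simple paired t-test". The SAP (Statistical Plan and Power) and the protocol (Statistical Considerations) give the same inputs: n=60, two-sided alpha 0.05, and 80% power for Cohen's d down to 0.38. Both cite a meta-analysis whose results "yield normalized effect sizes for IL-6 and TNF- α at 0.35 and 0.28, respectively", and a pilot estimate of 1.13 for ccf-mtDNA.

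They differ in how the conclusion is attached:

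- **Protocol:** the conclusion is a dependent clause of the ccf-mtDNA sentence: "such that we will be sufficiently powered to detect stress-induced changes".
- **SAP:** the conclusion is a new sentence, placed after all three effects and naming none of them: "we were sufficiently powered to detect stress-induced changes".

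Both then appeal to the repeated measurements. The SAP says that by modelling them "we would increase the power of the analysis to detect a change". The protocol goes further: "and so we expect to be amply powered". Neither gives variance components, a time course or a simulated power.

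**The concern.** On the SAP's own numbers, 0.35 and 0.28 are smaller than 0.38, so 80% power is not shown for either cytokine. A general statement of sufficiency does not follow from the figures just before it.

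The cytokines are not incidental. Both are listed outcomes of the mixed-model analysis, and Specific Aim 1 in the protocol expects a rise in ccf-mtDNA "which will statistically mediate subsequent peak circulating IL-6 and TNF- α levels". A reader told that the study was sufficiently powered could take a non-significant TNF-alpha result as evidence that there was no response. The data would often not support that reading.

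**Working it through.** **Inputs.** n = 60, each participant tested under both conditions ("We plan to recruit 60 non-smoking volunteers", protocol, Scientific Background). Paired t-test, two-sided alpha 0.05, target power 80%, and effects 0.35, 0.28 and 1.13 (SAP, Statistical Plan and Power).

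**Formula.** Power = P(|T| > t(0.975, 59)), where T is noncentral t with 59 df and noncentrality d√60, and t(0.975, 59) = 2.001.

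**The plan's own figure.** At d = 0.38 the noncentrality is 2.943 and power is 82.5%, against 80% stated. The effect detectable with 80% power is 0.368, against 0.38 stated. The difference is small and conservative. It does not affect the point, because 0.35 and 0.28 are below both values.

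**Power at the cited effects**

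| Outcome | d | d√60 | Power | Chance of a miss | n for 80% |
|---|---|---|---|---|---|
| ccf-mtDNA | 1.13 | 8.75 | >99.9% | <0.1% | – |
| IL-6 | 0.35 | 2.711 | 76.0% | 24.0% | 67 |
| TNF-alpha | 0.28 | 2.169 | 56.9% | 43.1% | 103 |

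A simulation of 40,000 paired samples agreed within 0.6 percentage points.

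**What a null result could exclude.** The 95% CI half-width is 2.001/√60 = 0.258 SD. A non-significant TNF-alpha result still includes 0.28 once the observed d exceeds 0.28 − 0.258 = 0.02. For IL-6, the interval still includes 0.35 once the observed d exceeds 0.35 − 0.258 = 0.09.

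**Sensitivity to the scale of the cited effects.** The documents do not say how the effects were standardised. The table above takes them as standardised by the SD of the paired difference.

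If they were standardised by the raw SD (assumption), the paired effect is d/√(2(1−r)), where r is the within-subject correlation:

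| r (assumed) | IL-6 | TNF-alpha |
|---|---|---|
| 0.3 | 62% | 44% |
| 0.5 | 76% | 57% |
| 0.7 | 93% | 79% |
| 0.8 | 99% | 92% |

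Power of 80% requires r = 1 − 0.5(d/0.3677)², which is 0.55 for IL-6 and 0.71 for TNF-alpha.

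If they are one-session pre-post effects, and the two sessions' changes have equal variance and are uncorrelated (assumption), the stress-minus-control effect is d/√2. That gives 0.247 and 0.198, with power 47% and 33%.

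**What the repeated measures would have to deliver.** To reach 80%, the SD of the stress-control contrast must fall by 1 − d/0.3677: 4.8% for IL-6 and 23.9% for TNF-alpha. As an illustration, average the four samples at 45, 60, 75 and 90 minutes, assuming a constant effect over them and independent within-day residuals. If w is the within-day residual share of the single-time contrast variance, averaging multiplies that variance by 1 − 0.75w. The requirement is w ≥ (1 − (d/0.3677)²)/0.75, which is 12.5% for IL-6 and 56.0% for TNF-alpha.

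**The case against.** The strongest reply is that the SAP sentence comes straight after the ccf-mtDNA effect and can be read as a conclusion about ccf-mtDNA alone. The protocol wording suggests this was the intent, and on that reading the sentence is true. But the SAP sentence names no outcome, refers to changes in general and closes a list of three effects. If the narrow reading is meant, the correction simply restores it.

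Second, the paired t-test is an openly declared stand-in, and the mixed model may well have more power. That is fair: the gain is not excluded. Nor is it established. For IL-6 the gain needed is small and plausible; for TNF-alpha it is large enough that it should be shown.

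Third, the percentages depend on an effect scale that cannot be checked from the documents. This stands as a limit on the exact figures, and the ranges show it. The comparison with 0.38 is the plan's own, however, and on that comparison both cytokines fall short.

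Fourth, power for a mean cytokine change is not power for mediation, and the protocol gives a separate correlation basis (0.35) for secondary analyses. That is correct, so the figures here concern only detection of the cytokine responses. Finally, the protocol's stronger phrase is worded as an expectation and names no cytokine. It does, however, follow the same three effects in the text on the Aim 1 primary analysis, so a reader will apply it to all of them.

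**Conclusion.** The concern holds: the SAP sentence is wrong as written. On the plan's own basis, n=60 is more than adequate for ccf-mtDNA (over 99.9%), about 4 points short of 80% for IL-6 (76.0%) and about 23 points short for TNF-alpha (56.9%). TNF-alpha carries most of the weight.

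The cytokine figures assume effects standardised by the SD of the paired difference, all 60 participants contributing both sessions, and no multiplicity adjustment. Under the other scales examined, power runs from 47% to 99% for IL-6 and from 33% to 92% for TNF-alpha. Adequate power for the cytokines is therefore possible, but the documents do not demonstrate it. The error is one of stated power only; the design and model are not in question here. It should be fixed.

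**What to change.** 1. In the SAP, limit the sentence to ccf-mtDNA and state the cytokine powers. For example: *With N=60, power to detect a ccf-mtDNA effect of d=1.13 exceeds 99.9%. Paired t-test power is 76% for IL-6 (0.35) and 57% for TNF-alpha (0.28), assuming these effects are standardised by the SD of the paired difference. The gain from the mixed model has not been quantified.*
2. State the scale on which the meta-analytic effects were standardised.
3. In the protocol's Statistical Considerations, make clear that the expectation of ample power does not cover the cytokines, unless a simulation of the planned mixed model, with stated variance components and time course, supports it.
4. Report the cytokine results with confidence intervals, and do not read a null TNF-alpha result as evidence of no effect.

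The cost is wording. No participants are added and no model or outcome changes. A simulation is needed only if the broader claim is kept for the cytokines. The downside is a less favourable power statement.
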